10.3 Analysis of secondary endpoints

We will obtain pathology reports from all surgical specimens and tabulate the data to obtain rate of pathologic CR. Descriptive reports of pathology findings for each cohort will also be reported. We will estimate progression-free survival probabilities using the Kaplan-Meier method. Progression-free survival is defined as the time from the first dose of nivolumab until progression or death from any cause. Toxicities will be categorized by frequency and type, and reported in tabular form for each cohort and all subjects on the trial. All patients will be evaluable for toxicity from the time of their first treatment with any study therapy.

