The primary objective of this study is to assess safety and feasibility of pre-operative nivolumab in patients with squamous cell carcinoma of head and neck (SCCHN) who will undergo surgery. The study will enroll a total of 26 patients and include patients with primary untreated, newly diagnosed SCCHN (Cohort 1), or patients with recurrent/metastatic SCCHN Cohort 2). Patients with primary untreated locoregional disease will undergo surgical resection as originally planned, right after study treatment. Patients with recurrent/metastatic disease will also be enrolled ideally if disease can be resected, but distant metastatic disease is acceptable if an indication for surgery is clinically appropriate (e.g. for symptomatic control, or if a distant lesions is addressed separately (e.g. SBRT or resection, or with further palliative treatment). In such patients distant metastatic disease can be addressed at an interval with systemic therapy or other local therapy/ies (RT, metastectomy) as indicated. All patients will be treated with 1 dose of nivolumab 480mg IV over 30 minutes 4-6 weeks prior to surgery. Subjects who sign the consent form but do not initiate protocol treatment for any reason (e.g., subjects who are screen failures), and patients who do not undergo surgical resection (for reasons unrelated to the study drug or toxicity) will be replaced and will not count towards the accrual goal.

Overall study design

The **primary objective** is to establish safety and feasibility of preoperative treatment with immune checkpoint inhibitor in patients with newly diagnosed or recurrent or metastatic SCCHN undergoing surgery.

Secondary objectives are to 1) determine the pathologic response using immune related response criteria (irPRC)⁵¹, 2) determine the changes in tumor-specific T cell responses and tumor microenvironment and compare these with baseline analyses in similar populations of patients undergoing resections without neoadjuvant therapy, 3) compare immunologic parameters between locoregional untreated and recurrent/metastatic sites, 4) compare irPRC⁵¹ with radiographic evidence of response to immunotherapy, and 5) determine progression free survival.

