1.2 Secondary Endpoints

- 1) Immune related pathologic response (irPRC)
→ irPRC criteria⁵¹ will be used – to assess resection specimen
- 2) Major pathologic response (MPR)
- 3) Progression free survival
Progression-free survival will be measured from the time of start of neoadjuvant nivolumab until radiologic or clinical progression or death.
- 4) Radiographic response rate
Response will be determined by RECIST version 1.1.

Exploratory

1. To determine changes in expression of selected immune markers and responses compared to baseline, in the blood, primary tumor tissue and draining lymph nodes from patients receiving neoadjuvant therapy; to determine changes in the quality and quantity of tumor infiltrating lymphocytes; and to compare findings in tumor and draining lymph nodes from treated patients, to findings in a parallel stage-matched cohort of untreated patients on a companion tissue collection protocol
2. To evaluate the potential effects of neoadjuvant therapy on normal head and neck mucosal tissue, by comparing tissues obtained on this study to those obtained from untreated patients undergoing tumor resection on a parallel tissue collection protocol.
- .
3. To compare immunologic markers and responses in HPV+ vs HPV(-) tumors. This includes

Johns Hopkins Protocol #: J1923

responses to HPV16 E6 and E7 antigens in patients with HPV+ cancers.

4. To explore features of the gut and oral microbiota of SCCHN patients before and after neoadjuvant nivolumab that may correlate with pathologic response.
5. To response to immunotherapy from pre- and on-treatment tissues in a histoculture model.
6. To assess recurrence-free survival in patients receiving preoperative therapy in this study.
7. To assess overall survival in high-risk patients with SCCHN receiving neoadjuvant therapy.
8. To study response to metabolic and or immunotherapy from pre- and on-treatment tissues in functional models (histocultures (slices/explants) and short term (< 4 weeks) in-vitro organoids) with in-vitro antibody testing.
9. To assess baseline immune and genomic tumor characteristics by performing multiplex immunofluorescence/immunochemistry (e.g., CD45, CD3, CD4, CD8, PDL1, etc.) and genetic sequencing (targeted and whole exome) on tissues slides/cryopreserved tissue blocks.

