4.1.2 Early salvage treatment options: salvage surgery, salvage chemotherapy

In patients with clinically worsening disease, or concern that resectability may be at risk, or due to extenuating scheduling circumstances, an earlier surgery date can be approved in consultation with the treating surgeon, medical oncologist, and study team.

Alternatively, neoadjuvant chemotherapy can be given in patients with clinically worsening disease, or concern that resectability may be at risk after approval and review by the treating surgeon, and medical oncologist, and study team.

Such 'salvage' patients will continue on study, unless deemed non-evaluable for other reasons.

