9. MEASUREMENT OF EFFECT

9.1 Pathologic evaluation

Assessment of immune related pathologic response (irPRC) is the first secondary endpoint of the study as defined by Stein et al.⁵¹

Diagnostic pathology specimen will be collected and processed following the treating institution's standard operating procedures and will be evaluated by a head and neck pathologist.

Major pathologic response (mPR) will also be assessed and is defined as $\leq 10\%$ residual tumor

tissue on all reviewed specimens of each subject.

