10.1.2 Endpoints

Primary Endpoint

Safety and feasibility of neoadjuvant nivolumab administration in patients with newly diagnosed head and neck cancer and those with locoregional recurrence or oligometastatic disease undergoing surgical resection, measured by 1) frequency of drug-related adverse events occurring up to 100 days after the last dose of nivolumab or 30 days after surgery (whichever is longer), and 2) successful completion of preoperative treatment and proceeding to surgery without any extended treatment-related delays greater than 28 days from the preplanned day 0 (or 14 days from day +14).

Secondary Endpoints

Immune related pathologic response (irPRC)
As defined by Stein et al (CCR 2019)⁵¹

Major pathologic response rate

Defined as $\leq 10\%$ residual tumor in the resection specimen after neoadjuvant nivolumab

Progression-free survival

Progression-free survival will be measured from the time of initiation of nivolumab until radiologic or clinical progression or death.

Radiographic response rate

Response will be determined by RECIST version 1.1.

Laboratory correlates of immune activity and response

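### Section 10.3 commits only to an unlisted pathologic CR rate, does not name irPRC or MPR, and by default counts specimens resected after salvage chemotherapy as response to nivolumab

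*Combined protocol and SAP*

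**What the plan says.** **Endpoints.** Sections 1.2 and 10.1.2 both list irPRC and MPR as secondary endpoints. Section 10.1.2 calls the second a rate and defines it as at most 10% "residual tumor in the resection specimen after neoadjuvant nivolumab". Section 9.1 states that "immune related pathologic response (irPRC) is the first secondary endpoint of the study" and that MPR will be assessed as well. None of these sections mentions pathologic CR. The term is defined nowhere, and a pathologic complete response otherwise appears only in the lung-study background of section 2.3.

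**Analysis.** Section 10.3 gives one sentence on a pathologic rate: "We will obtain pathology reports from all surgical specimens and tabulate the data to obtain rate of pathologic CR". It adds: "Descriptive reports of pathology findings for each cohort will also be reported".

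**Who is counted.** Section 4.8 makes patients without resection non-evaluable for pathologic response. Section 4.1.2 says that "neoadjuvant chemotherapy can be given in patients with clinically worsening disease", and it allows the same where resectability might be lost. Of these salvage cases it says that such "patients will continue on study, unless deemed non-evaluable for other reasons".

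**The concern.** An analysis section should produce an estimate for each listed endpoint. This one names an estimate for an endpoint that is not listed and leaves the listed ones unnamed. A pathologic CR rate does not yield an MPR rate, because specimens with some residual tumor, up to 10%, count for MPR but not for CR.

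The second issue is attribution. A patient may receive nivolumab, then chemotherapy, then surgery, and the specimen reflects both treatments. If it enters the MPR numerator without a label, the reported rate is no longer what 10.1.2 describes. With about 12 resected patients per cohort, each reclassified patient moves the rate visibly. If the rule is left until results are known, the choice of which specimens to count is open to hindsight.

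**Working it through.** **1. Endpoint lists against the analysis text**

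| Quantity | 1.2 | 9.1 | 10.1.2 | 10.3 |
|---|---|---|---|---|
| irPRC | listed | first secondary endpoint | listed | not named |
| MPR | listed | to be assessed | listed as a rate, at most 10% residual tumor | not named |
| Pathologic CR | absent | absent | absent | the only rate named |

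**2. How a post-chemotherapy specimen is handled**

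- 4.1.2: the patient stays on study unless non-evaluable for another reason.
- 4.8: for pathologic response, lack of resection is the stated ground for non-evaluability. A patient resected after chemotherapy does not meet it.
- 10.3: every surgical specimen enters the tabulation.

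Together these imply that the specimen is counted. No section says whether it should be labelled, separated or scored as non-response for an endpoint that 10.1.2 ties to nivolumab.

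**3. Size, on assumed counts**

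The plan gives no rate, precision or power for pathologic response, so there is no figure of its own to reproduce. The interval method can be checked on the 10.2 toxicity table. Clopper-Pearson 95% limits for x of n are the 2.5% quantile of Beta(x, n−x+1) and the 97.5% quantile of Beta(x+1, n−x). For 2/12 they give 2.1% to 48.4%, as printed there.

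The cohort size of 12 resected patients is from 10.2. Assume that the all-resected count is 3 MPR and that one patient had chemotherapy before surgery.

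| Handling | Rate | Exact 95% CI |
|---|---|---|
| Counted as 10.3 implies | 3/12 = 25.0% | 5.5–57.2% |
| Chemotherapy patient was a responder, shown separately | 2/11 = 18.2% | 2.3–51.8% |
| Chemotherapy patient was a responder, scored as no MPR | 2/12 = 16.7% | 2.1–48.4% |
| Chemotherapy patient was not a responder, shown separately | 3/11 = 27.3% | 6.0–61.0% |

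One reclassified responder is worth 1/12 = 8.3 points in a cohort, 1/24 = 4.2 points over two cohorts of 12, and 1/26 = 3.8 points over 26 patients. Separating the specimens can move the rate down (25.0 − 18.2 = 6.8 points) or up (27.3 − 25.0 = 2.3 points).

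Next, fix 2 nivolumab-only responders in a cohort of 12 and let 1, 2 or 3 further responders arise after chemotherapy:

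| Post-chemotherapy responders | Counted | Separated | Scored as no MPR |
|---|---|---|---|
| 1 | 3/12 = 25.0% | 2/11 = 18.2% | 2/12 = 16.7% |
| 2 | 4/12 = 33.3% | 2/10 = 20.0% | 2/12 = 16.7% |
| 3 | 5/12 = 41.7% | 2/9 = 22.2% | 2/12 = 16.7% |

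If no patient receives chemotherapy before surgery, all handlings agree.

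**The case against.** The strongest reply is that this is a wording slip. MPR is defined as a rate inside the statistics chapter, 9.1 says it will be assessed, 9.2.4.1 assigns irPRC scoring to a trained pathologist, and the descriptive sentence in 10.3 has room for both. That stands against any inference that the endpoints were abandoned. It does not supply an MPR estimate, a denominator or an interval in the section meant to give them.

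A reader might infer several stronger points that the documents do not support:

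- **That post-chemotherapy specimens have no rule.** There is an implicit default: they are counted. The fault is that it is unlabelled and sits badly with the MPR definition.
- **That the denominator is missing.** Section 4.8 gives it; 10.3 only fails to cite it.
- **That every chemotherapy patient had failed nivolumab.** Section 4.1.2 also permits chemotherapy over a resectability concern. Scoring all such patients as no MPR could itself misclassify some, so separation is the safer main display.
- **That the comparison of irPRC "with radiographic evidence of response to immunotherapy" is distorted.** This is not shown. Sections 4.1.1, 4.2.4 and 4.10 place imaging in the week before surgery, so scan and specimen could both follow chemotherapy. Section 9.2 speaks of imaging after 4 weeks of therapy, which could give a different order.
- **That the resected-set rate is biased because it cannot fall below an all-dosed rate.** That ordering follows from scoring every added or reclassified patient as no MPR. It is not evidence of bias.

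**Conclusion.** The point holds in two parts. First, 10.3 names a rate for an unlisted quantity and omits the two listed pathologic endpoints. This rests on the text alone and is certain. Second, following the text counts responses after salvage chemotherapy as responses to nivolumab. The mechanism is clear, but its size is not: the documents give no expected number of such patients, and every count used here is an assumption. One post-chemotherapy responder scored as no MPR is worth 8.3 points in a cohort of 12, with widely overlapping intervals. This is a problem of definition and not a difference that the trial could detect. The primary safety and feasibility analyses and the sample size are unaffected. The change should be made, but the trial does not depend on it.

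**What to change.** In 10.3, replace the pathologic CR sentence with text to this effect:

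> The MPR rate will be reported by cohort with an exact 95% CI. irPRC results will be reported by cohort as scored under the cited criteria. Pathologic CR will be reported descriptively. The denominator is the set of resected patients described in section 4.8. The MPR rate will be shown for all resected patients and, beside it, for patients who had nivolumab only before surgery, with post-chemotherapy specimens shown separately. The numbers of non-resected and post-chemotherapy patients will be listed with reasons.

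The exact interval is the method already used in 10.2. It is attached to the MPR rate only, because the documents do not show on what scale irPRC is scored. An all-dosed MPR rate, counting non-resected and post-chemotherapy patients as no MPR, is an optional sensitivity figure on the one-dose population of 10.2. It is conservative and should not replace the 4.8 rate.

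The cost is a few sentences, one extra table, and possibly a less favourable MPR rate. Nothing here bears on when chemotherapy or surgery is given.

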11. BIOMARKER, CORRELATIVE, AND SPECIAL STUDIES

(Please see lab manual for full details. The lab manual will be continually updated, and in case of discrepancies for specific items (e.g. a specific tube color) the lab manual will be followed as long as it is consistent with the intent of the protocol.

Five categories of exploratory correlative immune responses will be analyzed:

- 1) Expression of molecules in the tumor microenvironment (TME) via IHC and multispectral imaging of immunofluorescence staining (IF),
- 2) Analysis of T cell responses in peripheral blood to mutation associated neoantigens (MANA) and HPV-16 E6 and E7,
- 3) Flow cytometry and single cell analysis of TIL
- 5) Genomic markers assessed via Exome sequencing and RNAseq used to assess MANA and HPV specific immune responses.

Examples of membrane immunomodulatory molecules to be analyzed by IHC/IF as well as flow cytometry include, but are not limited to, PD-L1, PD-1, LAG3, TIM3, TIGIT, PVR Ig. The neoadjuvant trial design also allows for the isolation of enough TIL to analyze coordinate expression of multiple membrane and intracellular molecules by multiparameter flow cytometry as a complement to IHC/IF. Multiparameter flow cytometry analysis of TIL will utilize a 25-color T cell staining panel that can be assessed on the BDnSymphony50, which currently simultaneously analyzes 28 colors and will have the capability to analyze 48 colors in 2019. Competing multiplex flow cytometers have achieved similar results (e.g. Cytek Aurora). In addition to cell membrane receptors and ligands, a number of transcriptional activators and repressors have been associated with the anergic or “exhausted” T cell functional state vs an active effector or effector-memory state. For example, Tbethi Eomeslo cells represent renewable effector memory cells where as TbetloEomeshi cells are terminal cells on their way to full exhaustion or apoptosis. Other more recently defined transcriptional regulators, such as TCF-1, are important in maintenance of effector function.

Comprehensive genomic, transcriptomic and neoantigen analyses in tumor biopsies will be performed and MANA and HPV E6/7 antigen recognition will be analyzed via the MANAFEST assay for MANA and the VIRAEST assay for HPV. Whole-exome sequencing utilizing the Personal Genome Diagnostics (PGDx) next-generation platform will be utilized and performed on pre-treatment and resected tumor samples. This will allow detection of mutations in DNA-

repair and other relevant genes. Exome data will be applied in a neoantigen prediction pipeline that evaluates antigen processing, MHC binding and gene expression to generate neoantigens specific to the patient's HLA haplotype. Truncal neoantigens will be identified by correcting for tumor purity and ploidy. Putative neoantigens will then be used to generate peptides and stimulate autologous T cells, followed by T Cell Receptor (TCR) next-generation sequencing (MANAFEST).

The MANAFEST assay will determine if treatment increases the frequency and/or magnitude of anti-tumor T cell responses, based on the parameters described above. For each patient, the comparison of MANA-specific T cell clonality pre-and post-treatment among the peptides that are positive at both time points will be analyzed using a paired-sample t-test, and the difference of clonality of peptides that were MANAFEST-positive at either time points will be assessed using a mixed effect model to account for the correlation of common peptides. The analysis of MANAFEST results across patients will apply mixed effect models with each patient as a cluster, to account for the correlations due to the common microenvironment within a patient. Data transformation will be considered if the distribution of MANAFEST data is not normal. The VIRAFEST assay is an adaptation of the MANAFEST that analyzes T cell responses to predicted viral antigens in the identical fashion. For patients on this protocol with HPV+ HNSCC, we will analyze responses to a set of HPV-16 E6 and E7 peptides in addition to MANA peptides identified via WES.

11.1 Collection of tumor tissue specimens

11.1.1 Collection of pretreatment tumor and/or lymph node biopsies

Archived FFPE specimens from the original diagnostic tumor biopsy may be utilized. If archival tissue does not provide sufficient material for study, then new biopsies is recommended as clinically feasible. Ideally 6 (and at least 4) core needle biopsies of the tumor will be required at the time of diagnosis (prior to first dose of study drug) and in the event of a recurrence if clinically feasible; fine needle aspiration biopsy is sufficient for hilar or mediastinal lymph node sampling, but not for primary tumor biopsy. Where possible, and after a consent form has been signed, attempts will be made to coordinate diagnostic and study biopsies.

Previously collected tissue/blood/material can be accessed for this study to fulfill study requirements including fresh/frozen/FFPE/etc biologic material to fulfill eligibility/study requirements.

11.1.2 Pretreatment biopsy handling, transportation, storage and processing

Please see flow diagram in [Appendix B](#) for overview of tissue collection and the laboratory manual for detailed procedures. The study staff will be notified when a biopsy is taking place. The following procedures will be followed:

If a core needle biopsy is being performed specifically for entry to the study, then at least four

(and ideally 6) core-biopsy specimens will be obtained, the first 3-4 of these cores obtained will be suspended in 10% buffered formalin while subsequent cores will be flash frozen in liquid nitrogen (see lab manual). After approximately 24 hours of suspension in formalin, the cores will be embedded in paraffin. As required for correlative analyses slides will be cut for the appropriate studies listed below. For fine needle aspiration biopsies of lymph nodes from bronchoscopy, cells will be collected by centrifugation, fixed in formalin and embedded in a paraffin block using standard pathology procedures.

The study coordinator will keep a log with the study number, the patient's study number, the date and time, and a consecutive sample number; thus, the samples will be numbered serially and will not contain identifying information.

11.1.3 Surgical specimens (tumor and lymph nodes)

Tissue specimens obtained at the time of surgery will be dissociated enzymatically into single cell suspensions and will be viably cryopreserved according to a protocol provided in a companion laboratory manual. Additional specimens will be fixed in formalin and embedded in paraffin blocks, for routine pathologic studies and immunohistochemistry. Tissue will also be flash-frozen at -80°C for subsequent RNA/DNA analysis. If there is additional tissue available, it will be embedded in OCT (Optimal Cutting Tissue) compound for analysis of frozen sections.

11.2 Collection of blood samples

11.2.1 Collection schedule

Blood samples will be drawn and collected at the time points shown in the study calendar (section 4.10). These time points include:

Day -28 (Prior to treatment): 100 mL whole blood or local protocol for collection accepted for peripheral blood mononuclear cell (PMBC) isolation, and 20 mL whole blood for serum isolation
Day 0 (prior to surgery): 100 mL and 10 mL whole blood, for PBMCs and serum, respectively

11.2.2 Specimen handling, transportation, storage and processing

- Serum samples: Whole blood will be collected in serum tubes, processed per manufacturer's instructions and stored at -70°C or below until transfer for analysis.
- PBMCs: Whole blood will be collected into EDTA tubes (Becton-Dickinson ETDA tube or equivalent) and processed per manufacturer's instructions. Viable PBMCs will be stored in cryopreservation medium, at 5-10 ul per vial, in liquid nitrogen.

Analysis of exploratory features of oral and gut microbiota that correlate with clinical response.

Integration of microbiome science into cancer therapeutics is a new field of study. Three recent papers published in Science have suggested that responses in melanoma and lung cancer are impacted by the composition of the microbiome and that certain bacterial species can promote improved therapeutic responses to checkpoint inhibitor therapy⁴⁷⁻⁴⁹ (). Thus, the goal of this sample collection is to facilitate exploratory, correlative analyses between the oral and gut microbiome communities and responses to neoadjuvant checkpoint blockade therapy.

We will consider using 16S rRNA, shotgun metagenomics and/or RNA-seq for analyses. 16S rRNA sequencing data will be filtered for poor quality and contaminant/chimeric sequences, followed by taxonomic assignment using standard bioinformatic pipelines such as QIIME and Resphera Insight. To detect differentially abundant taxa between responders and non-responders, we will utilize the nonparametric Mann-Whitney test with correction for multiple hypothesis testing using the False Discovery Rate. To evaluate beta-diversity between responders and non-responders (i.e. shared total community composition), we will compute the UniFrac distance metric for all sample pairs, followed by principal coordinate analysis and significance testing with PERMANOVA⁵⁰. Functional inference of gene content from 16S rRNA data may also be performed using tools such as PICRUSt. While 16S rRNA identifies only bacterial sequences, metagenomics permits detection of viruses and fungi among others. Metagenomic analyses will be designed to remove human contaminant sequences followed by taxonomic assignment using Kraken and Pathoscope. Functional characterization of metagenomic data will be performed using the HUMAnN tool. Additionally, RNA-seq analysis (meta-transcriptomics) enables characterization of actively transcribed microbial genes and RNA viruses, with the potential to explore the combined host:microbial interaction(s).

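### The exploratory microbiome tests compare responders with non-responders without defining response, and split an outcome that could be analysed as percent residual tumor with more power

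*Combined protocol and SAP*

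**What the plan says.** Exploratory objective 4 in section 1.2 looks for features of the gut and oral microbiota "before and after neoadjuvant nivolumab that may correlate with pathologic response". The analysis text in section 11.2.2 opens under a different label: "Analysis of exploratory features of oral and gut microbiota that correlate with clinical response". The taxon-level method follows: "To detect differentially abundant taxa between responders and non-responders, we will utilize the nonparametric Mann-Whitney test". Multiplicity over taxa is handled by an FDR adjustment. Beta-diversity is compared between the same two groups by UniFrac distance and PERMANOVA.

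Section 11.2.2 does not say what makes a patient a responder. It gives no FDR level, no number of taxa or prevalence filter, and no expected number of responders.

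Other sections offer several measures that could fill the gap:

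- Immune-related pathologic response (irPRC), in sections 1.2 and 9.1.
- Major pathologic response: "Major pathologic response (mPR) will also be assessed" (section 9.1), with a cut at 10% residual tumor or less.
- Pathologic complete response: section 10.3 will "tabulate the data to obtain rate of pathologic CR".
- Radiographic response: "Response will be determined by RECIST version 1.1" (section 1.2).

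No analysis of percent residual tumor as a continuous variable is planned.

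**The concern.** There are two separate problems.

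**The groups are not fixed.** A patient with a RECIST response need not have a major pathologic response, and the reverse is also true. The set of analysable patients can change as well. Pathologic response exists only for resected patients (section 4.8), whereas radiographic response needs only on-time imaging (section 9.2.1). Both the Mann-Whitney and the PERMANOVA groupings could therefore be settled after the data are seen.

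**The split discards information.** To decide whether a specimen has 10% residual tumor or less, the pathologist must form a percentage. Reducing it to yes or no treats 15% and 95% residual tumor as the same outcome. In a trial of about two dozen patients that loss is large. If responders are very few, it can also put a floor under the p-value that a multiplicity-corrected test cannot get below.

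At stake is whether the paired stool and oral samples yield an interpretable result. No primary or secondary endpoint depends on this analysis.

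**Working it through.** The plan states no power, effect size or FDR figure for this analysis, so there is none to reproduce.

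**Inputs from the documents**

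- Resected patients: 12 per cohort (section 4.1), so 2 x 12 = 24. The total is up to 26 (section 10.2).
- Cited response rates: MPR in 9/20 = 45% after two doses in lung cancer (section 2.3), and a pathologic response of unstated depth in 43% in head and neck cancer (section 2.3.1). In 24 patients these give 0.45 x 24 = 10.8 and 0.43 x 24 = 10.3 responders.

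**Assumptions**

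- Two-sided exact tests and Benjamini-Hochberg control at q = 0.05.
- 100 taxa where a single threshold is needed, so a lone taxon must reach 0.05/100 = 0.0005.
- For power: bivariate normal data, true correlation 0.6, and responders taken as the patients with the least residual tumor.

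**Step 1: power, split against unsplit (simulation, n = 24)**

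| Analysis | Power at 0.05 | Power at 0.0005 |
|---|---|---|
| Spearman, percent residual tumor | about 84% | about 27% |
| Spearman, half of the values tied | about 78% | about 20% |
| Mann-Whitney, 2 responders | about 30% | 0% |
| Mann-Whitney, 5 responders | about 51% | about 4% |
| Mann-Whitney, 10 responders | about 66% | about 8% |

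The row with 10 responders corresponds to the cited 43%, so the loss does not depend on assuming a low response rate.

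**Step 2: when the p-value floor matters**

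With k responders among n patients, the smallest exact two-sided Mann-Whitney p is 2/C(n,k). A lone taxon passes only if p <= q/T for T taxa tested, so T can be at most q x C(n,k)/2.

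| Responders of 24 | Smallest p | Most taxa at which a lone taxon can pass (q = 0.05) |
|---|---|---|
| 2 | 2/276 = 0.0072 | 6 |
| 3 | 2/2,024 = 0.00099 | 50 |
| 4 | 2/10,626 = 0.00019 | 265 |
| 10 | about 1.0e-6 | about 49,000 |

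With 26 patients the limits for 3 and 4 responders rise to 65 and 373. With q = 0.10 and 24 patients, 3 responders allow 101 taxa.

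**Step 3: how likely that is**

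The binomial chance of 3 or fewer responders among 24 is 79%, 50%, 26% and 4% at true rates of 10%, 15%, 20% and 30% (all assumed). It is about 0.1% at 43% to 45%. The documents give no MPR rate for one dose in this population. Section 2.3.1 says that the expected response in previously treated patients is unclear.

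**The case against.** A reader might infer that the planned test cannot declare any taxon whatever the data show. The documents do not support that. It needs about 3 or fewer responders, more than 50 taxa and a lone signal. With 3 responders and 100 taxa, two taxa both at the floor would pass, because 2 x 0.05/100 = 0.0010 exceeds 0.00099. At the cited 43% to 45% the floor is irrelevant. The FDR level and the number of taxa are assumptions here, since the plan states neither.

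A reader might also work out the floor inside one cohort of 12, where even a 6/6 split gives p no lower than 2/924 = 0.0022. Section 11.2.2 does not say that the taxon tests are run within cohort, so that calculation addresses an analysis the plan does not state.

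Other fair points on the plan's side:

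- The analysis is labelled exploratory, and Mann-Whitney with FDR control is a legitimate method. PERMANOVA is one global test without the per-taxon burden. This limits the severity. It does not supply the missing definition of response, which both tests need.
- Recording of a continuous percentage is inferred from the 10% cut-off and is not stated. This stands, so the fix has to ask for it.
- Residual tumor may pile up at 0% or 100%. This stands in part: with half of the values tied, Spearman still has about 78% power at 0.05, above every Mann-Whitney row.
- Spearman is itself weak at FDR-level thresholds, at about 27%. This stands. The change improves the analysis but does not make a null result for a single taxon informative.

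**Conclusion.** The point holds as a matter of definition and efficiency. The inconsistency between pathologic response in section 1.2 and clinical response in section 11.2.2, with responders undefined in the tests, is in the text and needs no assumption.

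The loss from splitting is large at nominal significance: about 84% power against 30% to 66%. At a threshold of 0.0005 it is about 27% against 0% to 8%. These figures rest on n = 24, a true correlation of 0.6 and bivariate normal data, and heavy ties reduce the gain.

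Outright inability to declare a lone taxon is a conditional risk confined to very few responders. At the response rates the documents cite, the problem is lost power. Because the analysis is exploratory, this should be corrected, but it does not threaten the trial's main conclusions.

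**What to change.** In section 11.2.2:

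- Name pathologic response as the outcome, and replace clinical response in the heading so that it agrees with exploratory objective 4.
- Require percent residual tumor in the resection specimen to be recorded as a number for each resected patient.
- Make the main taxon-level analysis a Spearman correlation of taxon abundance with percent residual tumor, keeping the FDR correction. State the FDR level and the rule for which taxa are tested.
- Use percent residual tumor as the predictor in PERMANOVA.
- Keep the Mann-Whitney comparison of MPR with non-MPR patients as descriptive.

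The cost is a few sentences and one recorded value per patient. No added patients, samples or assays are needed. The report should say how many residual-tumor values are tied, and that failure to find a single taxon is weak evidence at this sample size.
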